8.2.1.4 Time Period and Frequency of AE and SAE Reporting

The Investigator will report all AEs from the time informed consent was obtained until the final protocol-defined study visit or last known dose date of study drug + 1 day, whichever is later.

The Investigator will report all SAEs from the time informed consent was obtained until 30 days after the last known dose date of study drug.

At each visit, patients are to be queried regarding any AEs that have occurred since the previous visit. Patients will be asked to volunteer information with a nonleading question such as, "How do

you feel since your last visit?"

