9.4.5.1 Adverse Events

Adverse events will be recorded for each patient from the time informed consent was obtained until the final protocol-defined study visit or the last known dose date of lumateperone + 1 day.

SAEs will be reported from the time informed consent was obtained until 30 days after the last known dose date of lumateperone.

Adverse events will be coded by system organ class (SOC) and preferred term using the Medical Dictionary for Regulatory Activities (MedDRA).

An AE that occurs during the Open-label Treatment Period will be considered a treatmentemergent AE (TEAE) if it starts as a new event or if its severity increases during the Open-label Treatment Period. An AE that occurs more than 1 day after the date of the last dose of open-label lumateperone will not be counted as a TEAE.

The number and percentage of patients reporting TEAEs will be tabulated by system organ class (SOC) and preferred term; by SOC, preferred term, and severity; and by SOC, preferred term, and relationship to study drug. If more than one AE is coded to the same preferred term for the same patient, the patient will be counted only once for that preferred term using the most severe and most related occurrence for the summary by severity and by relationship to study drug.

Additional details pertaining to analyses of AE data will be provided in the SAP.

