2. INTRODUCTION

This statistical analysis plan (SAP) provides the technical and detailed elaboration of the statistical analyses of the efficacy and safety data as outlined and/or specified in the Protocol Amendment 1 (dated 23 Aug 2021) of Study ITI-007-503.

Study ITI-007-503 ("Study 503") is an international, open-label, multicenter, 6-month study to assess the safety and tolerability of lumateperone as adjunctive therapy in patients with MDD. The Study will be performed at approximately 120 study centers. No *de novo* patients will be enrolled.

Patients who have safely completed the lead-in studies may be eligible to participate in this Open-label Safety Study. Lead-in study completion is defined as a patient who completes the double-blind treatment period (ie, all scheduled visits up to and including Visit 8) of the lead-in study.

The study will be conducted as follows:

- A Screening Period of one day in duration. Potential patients rolling over from the lead-in studies will be evaluated for eligibility during the Screening/Baseline Visit (Visit 1/Day 1) which is the same visit as Visit 8/Day 43 of the lead-in study. Patients who meet all eligibility criteria at the Screening/Baseline Visit (Visit 1/Day 1) will be dispensed lumateperone 42 mg to be self-administered each evening without respect to food.
- A **26-week Open-label Treatment Period** during which patients will self-administer lumateperone, to be taken each evening, without respect to food. Background ADT should also continue as previously prescribed, with no change of dose from the lead-in studies. Patients will attend visits on Weeks 1, 2, 3, 4, 6, 8, 10, 12, 14, 16, 18, 20, 22, 24, and 26. The Open-label Treatment Period will last a total of 26 weeks. A patient will be defined as a treatment completer if the patient completes the Open-label Treatment Period (all scheduled visits up to and including Visit 16/Week 26).
- A 2-week Safety Follow-up Period. A Safety Follow-up visit will occur approximately 2 weeks after completion of the Open-label Treatment Period or after the Early Termination (ET) Visit. Any ongoing AEs at the Safety Follow-up Visit must be followed until resolution, until the AE stabilizes, until it is determined to be not clinically significant, or until the patient is lost to follow-up.

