10.1 Adverse Events

Adverse events will be coded by system organ class (SOC) and preferred term (PT) using the Medical Dictionary for Regulatory Activities (MedDRA).

An AE that occurs during the Open-label Treatment Period will be considered a treatmentemergent AE (TEAE) if it starts as a new event or if its severity increases during the Open-label Treatment Period. An AE that occurs more than 1 day after the date of the last dose of open-label lumateperone will not be counted as a TEAE.

The number and percentage of patients reporting TEAEs will be tabulated by system organ class (SOC) and PT; by SOC, PT, and severity; and by SOC, PT, and relationship to study drug. If more than one AE is coded to the same preferred term for the same patient, the patient will be counted only once for that preferred term using the most severe and most related occurrence for the summary by severity and by relationship to study drug.

The incidence of common (\geq 5% of patients) TEAEs will be summarized by preferred term and treatment group.

The number and percentage of patients reporting serious AEs (SAEs) during the Open-label Treatment Period will be tabulated by SOC and PT. Also, the number and percentage of patients reporting AEs leading to drug withdrawal will be tabulated by SOC and preferred term. Listings will be presented for patients with SAEs, patients with AEs leading to drug withdrawal, and patients who died.

The incidence of extrapyramidal symptom (EPS) TEAEs will be summarized by PT and treatment group and will be sorted by decreasing frequency. The PTs for EPS will be based on Broad and Narrow Standardised MedDRA Queries (SMQs) as listed in Table 10-1. The analysis for EPS TEAEs based on Broad SMQs will also include the preferred terms listed under Narrow SMQs.

Confidential Page 18 of 40

Table 10-1: Preferred Terms for Extrapyramidal Symptoms

Scope	Preferred Terms

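### SAEs are collected to 30 days after the last dose, but the only planned SAE count stops with the Open-label Treatment Period

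*SAP*

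**What the plan says.** **Collection.** Protocol 8.2.1.4 has investigators report SAEs from consent "until 30 days after the last known dose date of study drug". The statistics section, Protocol 9.4.5.1, repeats this: "SAEs will be reported from the time informed consent was obtained until 30 days after the last known dose date of lumateperone".

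**Tabulation.** SAP 10.1 gives one SAE incidence table, worded as "serious AEs (SAEs) during the Open-label Treatment Period will be tabulated by SOC and PT". The TEAE tables do not reach further: "An AE that occurs more than 1 day after the date of the last dose of open-label lumateperone will not be counted as a TEAE".

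**Periods.** SAP 2 separates treatment from follow-up. On treatment: "The Open-label Treatment Period will last a total of 26 weeks". On follow-up: "A Safety Follow-up visit will occur approximately 2 weeks after completion of the Open-label Treatment Period", or after the Early Termination visit.

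**Other outputs.** SAP 10.1 also plans listings of patients with SAEs and of patients who died, with no period limit stated. SAP 10.5.4 tabulates suicidal ideation and behavior on the C-SSRS for Safety Follow-up as well as for treatment, and includes completed suicide in both.

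**The concern.** Safety is the primary objective, and Protocol 9.4.5.1 leaves further AE analysis detail to the SAP. The SAP then counts SAEs over a shorter window than the one in which they are collected. A reader of the report would find one SAE percentage. To learn how many patients had an SAE or died in the month after stopping, that reader would have to count rows in a listing.

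The SAP is also uneven. A suicidal act recorded at the follow-up visit enters a C-SSRS table with a percentage. The same act reported as an SAE is left out of the SAE table.

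Finally, the SAP does not say when the Open-label Treatment Period closes for SAE counting: at last dose, at last dose + 1 day, or at Visit 16/ET. The + 1 day rule is stated for TEAEs, not for the SAE table. Since an ET visit may fall some days after the last dose, two programmers could obtain different SAE counts for patients who stop early.

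**Working it through.** The documents state no SAE rate and no power calculation, so there is no planned figure to reproduce. The check compares the two windows.

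**Inputs.** Treatment period: 26 weeks = 182 days (SAP 2). SAE collection after last dose: 30 days (Protocol 8.2.1.4 and 9.4.5.1). Planned enrolment: about 760 (Protocol synopsis).

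**Uncounted days.** If the SAE table closes at last dose, 30 days go uncounted. If it closes at last dose + 1 day, 29 do. If it closes at an ET visit *d* days after the last dose, 30 − *d* do. So 29 to 30 days is the upper end.

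**Share of the collected window** = uncounted days ÷ (treatment days + 30):

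| Last dose on day | Collected days | 29 uncounted | 30 uncounted |
|---|---|---|---|
| 28 | 58 | 50.0% | 51.7% |
| 56 | 86 | 33.7% | 34.9% |
| 112 | 142 | 20.4% | 21.1% |
| 182 | 212 | 13.7% | 14.2% |

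Only the last row follows from the planned treatment length. The stopping days in the other rows are examples, since the documents give no dropout distribution.

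**Patient-time, upper bound.** If all 760 are dosed and followed, the tail is 760 × 29 ÷ 365.25 = 60.3 to 760 × 30 ÷ 365.25 = 62.4 patient-years. Full treatment time is 760 × 182 ÷ 365.25 = 378.7.

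**Effect on the percentage.** Each added patient with an SAE raises the incidence by 1 ÷ 760 = 0.13 percentage points. To illustrate, assume 760 dosed completers, a constant hazard, and an on-treatment SAE risk *r*. None of these assumptions comes from the documents. With *h* = −ln(1 − *r*) ÷ 182 and *u* = 29 or 30 uncounted days, the further patients with a first SAE number 760 × (1 − *r*) × (1 − exp(−*hu*)), and the combined incidence is 1 − exp(−*h*(182 + *u*)):

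| Assumed *r* | Further patients | Combined incidence |
|---|---|---|
| 1% | 1.20 to 1.25 | 1.16% |
| 2% | 2.39 to 2.48 | 2.31% to 2.33% |
| 4% | 4.73 to 4.89 | 4.62% to 4.64% |

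**The case against.** The strongest reply is that an on-treatment SAE proportion is an ordinary and legitimate quantity. The table states its own window, so events outside that window do not bias it. A proportion through last dose + 30 days is a different quantity. It includes off-drug time and, since Protocol 7.9 lets patients whose depression worsens be discontinued to start other treatment, possibly time on new therapy. This stands. A reader might infer that the planned SAE rate is biased low, but the documents do not support that. The table is incomplete relative to what is collected, which is a weaker statement.

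Second, late events are not hidden. The SAE and death listings carry no period limit, and C-SSRS events are tabulated for Safety Follow-up. AEs leading to drug withdrawal are tabulated with no stated period limit. Death is also a listed discontinuation reason (Protocol 6.4.1), so the disposition summary in SAP 5 would count deaths that end treatment. This stands too, with limits. A listing gives no percentage. The follow-up visit comes at about two weeks, so the C-SSRS does not span 30 days. The disposition summary concerns discontinuation from the treatment period only.

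Third, the study is single-arm and descriptive, and no decision rule is tied to the SAE percentage. This limits the consequence but does not remove the gap.

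Fourth, the last dose + 1 day cut-off for TEAEs is in Protocol 9.4.5.1 itself, and the SAP follows it. It is not a conflict between the documents, and the absence of a table of nonserious follow-up AEs is a matter of preference.

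**Conclusion.** The mismatch is confirmed. No SAE table, and no count of deaths apart from completed suicide on the C-SSRS, covers the post-treatment part of a window the protocol requires sites to report. The on-treatment table is valid as labelled, but it understates SAE incidence over the collected window.

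The tail is at most about 29 to 30 days per patient: about 14% of the collected window for a 26-week completer, and a larger share for early stoppers. Its exact length depends on a closing date that the SAP does not define for SAEs.

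The change in the rate cannot be known from the documents. The illustration gives roughly 0.2 to 0.6 percentage points for assumed on-treatment risks of 1% to 4%, and it rests wholly on a constant hazard and 760 dosed completers. A reader might infer that early stoppers are especially likely to have an SAE soon after stopping, and so that the true effect is larger. That is plausible reasoning, but the documents give no rate to support it, and the 50% share at day 28 is a share of days, not of events.

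This is a cheap improvement to completeness, not an error that invalidates the planned table.

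**What to change.** In SAP 10.1:

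- Keep the on-treatment SAE table and state when the period closes for SAE counting (last dose, last dose + 1 day, or Visit 16/ET).
- Add a column or companion table with the number and percentage of patients with SAEs, by SOC and PT, and the number and percentage of deaths, with onset from first open-label dose through last dose + 30 days.
- Leave the TEAE definition unchanged. No separate table of nonserious follow-up AEs is needed.

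The cost is one column or table built from data the protocol already collects, with no new visits. The added SAE percentage may be slightly higher than the on-treatment one. It should carry a footnote that it includes off-drug time and possibly time on new therapy.

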10.2 Clinical Laboratory Parameters

Descriptive statistics for clinical laboratory values (in SI and conventional units) and changes from baseline values at each assessment timepoint and at the end of the Open-label Treatment Period will be summarized for each clinical laboratory parameter:

- **Hematology:** hematocrit; hemoglobin; red blood cell count with indices (mean corpuscular volume, mean corpuscular hemoglobin, and mean corpuscular hemoglobin concentration); reticulocytes; white blood cell count and differential (neutrophils, lymphocytes, monocytes, eosinophils, and basophils) reported as percent (%) and absolute values; and platelet count.
- Chemistry: albumin; alkaline phosphatase; ALT; AST; bilirubin (total, direct); blood urea nitrogen; calcium; chloride; cholesterol (high-density lipoprotein [HDL] and low-density lipoprotein [LDL] will be calculated and reported); creatinine; creatine phosphokinase; gamma-glutamyl transferase; glucose; insulin; lactate dehydrogenase; phosphate; potassium; prolactin; sodium; triglycerides; total protein; uric acid; HbA1c; and TSH (reflex free T3 and free T4).
- Urinalysis: pH and specific gravity.

Clinical laboratory values are considered potentially clinically significant (PCS) values if they meet either the lower or upper criteria listed in Table 10-2. The number and percentage of patients with PCS postbaseline clinical laboratory values during Open-label Treatment Period will be tabulated. The percentages will be calculated relative to the number of patients with available non-PCS baseline values and at least 1 postbaseline assessment. The numerator will be the total number of patients with available non-PCS baseline values and at least 1 PCS postbaseline value during the Open-label Treatment Period. A supportive listing of patients who have PCS values will be provided and will include the PID number and baseline and postbaseline values for each patient. A listing of all AEs for patients with PCS clinical laboratory values will also be provided.

Confidential Page 20 of 40

Table 10-2: Criteria for Potentially Clinically Significant Clinical Laboratory Tests

Laboratory Parameter	Conventional Unit	PCS Criteria ^a Low Values	PCS Criteria ^a High Values		
Hematology					
Hemoglobin	g/dL	< 0.9 × LLN	_		
Hematocrit	%	< 0.9 × LLN	_		
Absolute neutrophil count (ANC)	10^3/μL	< 1.0	_		
Platelet count	10^3/μL	≤ 75	≥ 700		
White blood cell (WBC) count	10^3/μL	≤ 2.5	≥ 15		
Chemistry					
Albumin	g/dL	< 2.5			
Alkaline phosphatase	U/L	_	≥ 2 × ULN		
ALT	U/L	_	≥ 3 × ULN		
AST	U/L	_	≥ 3 × ULN		
Blood urea nitrogen (BUN)	mg/dL	_	≥ 30		
Calcium	mg/dL	< 7	> 12		
Chloride	mEq/L	< 90	> 115		
Total Cholesterol	mg/dL	_	≥ 300		
СРК	mg/dL	_	≥ 5 × ULN		
Creatinine	mg/dL	_	> 1.3 × ULN		
Glucose	mg/dL	< 45	> 160		
LDL Cholesterol	mg/dL	_	> 200		
Potassium	mEq/L	< 3	> 5.5		
Prolactin	ng/ml	_	> 200		
Sodium	mEq/L	< 130	> 150		
Total bilirubin	mg/dL	_	≥ 2 × ULN		
Total protein	_	< 0.9 × LLN	> 1.1 × ULN		
Triglycerides	mg/dL	_	≥ 300		
Uric Acid	mg/dL	_	> 1.1 × ULN		
Urinalysis					
Protein	_	_	At least 2 +		
Glucose	_	_	At least 2 +		
Blood	_	_	At least 2 +		

ALT = alanine aminotransferase; AST = aspartate aminotransferase; CPK=creatine phosphokinase; LLN = lower limit of normal of laboratory reference range; PCS = potentially clinically significant; ULN = upper limit of normal of laboratory reference range.

Confidential Page 21 of 40

^a Criteria refer to conventional units.

The number and percentage of patients with shifts from baseline at the end of Open-label Treatment Period according to normal range and PCS criteria (PCS Low, Low, Normal, High, PCS High) for each parameter will be provided if applicable.

The criteria for elevated liver function-related laboratory values are specified in Table 10-3. The frequency and percentage of subjects with treatment-emergent elevated liver function values during the Open-label Treatment Period will be summarized for each treatment group for the Safety Population.

Table 10-3: Elevated Liver Function Criteria

Liver Function Parameter	Criteria
	\geq 3 × ULN
ALT	\geq 5 × ULN
ALI	$\geq 10 \times ULN$
	\geq 20 × ULN
	\geq 3 × ULN
AST	\geq 5 × ULN
ASI	$\geq 10 \times ULN$
	\geq 20 × ULN
ALT or AST	\geq 3 × ULN
	\geq 5 × ULN
	$\geq 10 \times ULN$
	\geq 20 × ULN
Total Bilirubin	$\geq 1.5 \times ULN$
	\geq 2 × ULN
Alkaline phosphatase	$\geq 1.5 \times ULN$
	\geq 2 × ULN
Combined Elevation in ALT or AST, and Total	ALT or AST \geq 3 × ULN, Total
Bilirubin	Bilirubin $\geq 1.5 \times ULN$
	ALT or AST $\geq 3 \times ULN$, Total
	Bilirubin ≥ 2 × ULN
Hy's Law	Concurrent evaluation ^a :
	ALT or AST $\geq 3 \times \text{ULN}$, Total
	Bilirubin $\geq 2 \times ULN$, and Alkaline phosphatase $\leq 2 \times ULN$
	phosphatase > 2 ^ OLN

^a Concurrent assessments: analytes may come from multiple samples taken within a 24-hour period.

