7.4 Method of Assigning Patients to Treatment Groups

After a patient signs the ICF at Visit 1 of the Open-label Treatment Period, site personnel will register the patient in the interactive web response system (IWRS). All rollover patients will be identified using the same Patient ID that was assigned by IWRS in the lead-in study.

Lumateperone will be labeled with medication kit numbers. The IWRS will provide the study center with the specific medication kit number(s) for each eligible patient at the time of enrollment. Study center personnel will dispense lumateperone according to the IWRS instructions. Study center personnel will also log onto the IWRS at subsequent visits to obtain a kit number for dispensing lumateperone. Study centers will receive the IWRS confirmation notifications for each transaction. All notifications are to be maintained with the study source documents.

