9. STATISTICAL METHODS

9.1 General Considerations

The statistical analysis plan (SAP) will be finalized prior to database lock and will include a more technical and detailed description of the statistical analyses described in this section. This section is a summary of the planned statistical analyses of important endpoints including primary and key secondary endpoints.

Continuous variables will be summarized using descriptive statistics (number of patients [n], mean, standard deviation [SD], median, minimum, and maximum, unless otherwise stated). Categorical variables will be summarized using frequency counts and percentages.

The baseline for each specific efficacy/safety change-from-baseline analysis endpoint is defined as the last measurement prior to the first dose of study treatment from the lead-in study.

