9.2 CGI-S Score

A descriptive summary for the change from baseline to each assessment visit in CGI-S score will be provided for each scheduled visit.

Confidential Page 17 of 40

10. SAFETY ANALYSES

Safety analyses will be performed using the Safety Population. The safety parameters will include AEs, clinical laboratory, vital signs, ECG, and EPS (AIMS, BARS, and SAS) and C-SSRS scales. Baseline is defined as the last measurement prior to the first dose of double-blind treatment during the lead-in studies (Studies ITI-007-501 and ITI-007-502).

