10.3 Vital Signs

Descriptive statistics for vital signs (eg, supine pulse rate, supine systolic and diastolic BP, body weight) values at baseline and changes from baseline values at each assessment visit, and at the end of the Open-label Treatment Period will be presented.

Vital sign values will be considered PCS if they meet the criteria for both the observed value and the change from baseline value listed in Table 10-4. The number and percentage of patients with PCS postbaseline vital sign values during Open-label Treatment Period will be tabulated for the Safety Population. The percentages will be calculated relative to the number of patients with an available baseline value and at least 1 postbaseline assessment. The numerator will be the total

Confidential Page 22 of 40

number of patients with an available baseline value and at least 1 PCS postbaseline vital sign value. A supportive listing of patients with PCS postbaseline values will be provided and will include the PID number and baseline and postbaseline values for each patient. A listing of all AEs for patients with PCS vital sign values will also be provided.

Table 10-4: Criteria for Potentially Clinically Significant Vital Signs

Vital Sion Danameter mit	Elaa	Criteria ^a					
Vital Sign Parameter, unit	Flag	Observed Value	Change From Baseline				
Supine Systolic blood pressure, mmHg	High	≥ 180	Increase of ≥ 20				
Supine Systone blood pressure, mining	Low	≤ 90	Decrease of ≥ 20				
Suning Digetalia blood procesure, mmHg	High	≥ 105	Increase of ≥ 15				
Supine Diastolic blood pressure, mmHg	Low	≤ 50	Decrease of ≥ 15				
Supine Pulse rate, bpm	High	≥ 120	Increase of ≥ 15				
Supine Fuise rate, opin	Low	≤ 50	Decrease of ≥ 15				
Waighth	High	_	Increase of ≥ 7%				
Weight ^b	Low	_	Decrease of ≥ 7%				

bpm = beats per minute.

The number and percentage of patients with orthostatic hypotension during the Open-label Treatment Period will be provided for the Safety Population. Orthostatic hypotension is defined as a reduction of ≥ 20 mm Hg in SBP or a reduction of ≥ 10 mm Hg in DBP while changing from the supine to standing position. A supportive listing of patients with orthostatic hypotension during the Open-label Treatment Period and Safety Follow-up Period will be provided. A listing of all AEs occurring in patients who experienced orthostatic hypotension will also be provided.

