10.4 Electrocardiograms

Descriptive statistics for ECG parameters (eg, ventricular heart rate, QTc interval, QRS interval) at baseline and changes from baseline values at each assessment visit, and at the end of the Openlabel Treatment Period will be summarized.

ECG parameter values will be considered PCS if they meet the criteria listed in Table 10-5. The number and percentage of patients with PCS postbaseline values during Open-label Treatment Period will be tabulated for the Safety Population. The percentages will be calculated relative to the number of patients with baseline value (for criteria involving change from baseline) or non-PCS baseline value (for criteria not involving change from baseline), and at least 1 assessment during the open-label treatment period. The numerator will be the total number of patients out of those included in the denominator and with at least 1 PCS value during the Open-label Treatment Period. A supportive listing for all patients with PCS values will be provided, which will include the PID number and baseline and postbaseline ECG values for each patient. A listing of all AEs for patients with PCS ECG values will also be provided.

Confidential Page 23 of 40

^a A postbaseline value will be considered potentially clinically significant if it meets both criterion value and change from baseline.

b Weight change is relative to baseline.

Table 10-5: Criteria for Potentially Clinically Significant Electrocardiographic Values

D	Criteria ^a							
Parameter, unit	Value	Change from Baseline						
QRS duration, msec	≥ 150	_						
PR interval, msec	≥ 250	_						
QTcB, msec	≥ 480	_						
QTcB, msec	≥ 500	_						
QTcF, msec	≥ 480	_						
QTcF, msec	≥ 500	_						
QTcB, msec	_	> 30 and ≤ 60						
QTcB, msec	_	Increase of > 60						
QTcF, msec	_	> 30 and ≤ 60						
QTcF, msec	_	Increase of > 60						

PCS = potentially clinically significant; QTc = corrected QT interval; QTcB = QT interval/(RR)½; QTcF = QT interval/(RR)½.

Confidential Page 24 of 40

^a A post-baseline value will be considered potentially clinically significant if it meets the criterion value or the change from baseline value.

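### The laboratory PCS denominator in SAP 10.2 keeps patients who have no open-label test, so the rate is slightly understated; SAP 10.3 shares the wording

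*SAP*

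**What the plan says.** - **Baseline.** SAP section 10 sets one baseline for the safety analyses: "Baseline is defined as the last measurement prior to the first dose of double-blind treatment during the lead-in studies". Protocol 9.1 agrees: it is "defined as the last measurement prior to the first dose of study treatment from the lead-in study".
- **Laboratory denominator (SAP 10.2).** The rule is: "The percentages will be calculated relative to the number of patients with available non-PCS baseline values and at least 1 postbaseline assessment".
- **Laboratory numerator (SAP 10.2).** It counts "patients with available non-PCS baseline values and at least 1 PCS postbaseline value during the Open-label Treatment Period".
- **Vital signs (SAP 10.3).** The denominator again asks for a baseline value and one postbaseline assessment, with no period named. The numerator sentence reads "number of patients with an available baseline value and at least 1 PCS postbaseline vital sign value", also without a period. The sentence that introduces the table does limit it to the open-label period.
- **ECG (SAP 10.4).** The denominator requires a suitable baseline "and at least 1 assessment during the open-label treatment period". The efficacy set in SAP section 9 is limited to the open-label period in the same way.
- **PCS determination (SAP 15.2).** It is based on the assessments made in the open-label period.
- **Safety Population (SAP 4.2).** One open-label dose is enough; no later measurement is required.

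**The concern.** The two halves of the laboratory fraction refer to different periods. The numerator looks only at open-label values. The denominator condition can be met by a value taken before open-label treatment began, because baseline was set before the lead-in study.

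A patient who took open-label drug and left without a further laboratory test therefore stays in the denominator. That patient cannot enter the numerator and so is reported as free of abnormality.

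Safety and tolerability are the primary objective, and this error can only lower the laboratory rate. It also puts the laboratory and ECG tables of one report on different denominators without saying so.

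**Working it through.** The documents state no PCS rate and no calculation for this point, so there is no plan figure to reproduce.

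**Step 1: who meets the denominator condition.** Protocol 6.1 defines lead-in completion as attending all scheduled visits up to and including Visit 8, and says that Visit 8/Day 43 is the same visit as open-label Visit 1/Day 1. Protocol 8.2.4 uses the Visit 8 laboratory tests as this study's Screening/Baseline tests. Every rollover patient is thus scheduled for a laboratory test that comes after the analysis baseline and before the first open-label dose. The postbaseline condition removes almost nobody. Earlier lead-in visits may also supply values, but the lead-in schedule is not in these documents, so only Visit 8 is relied on here.

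**Step 2: who has no open-label value.** Laboratory tests during open-label treatment are scheduled at Visits 2, 7, 11 and 16/ET (protocol Table 1-1). Patients can miss all of these if they leave before Visit 2 and do not return for the ET visit, or if they are seen only remotely and no local test is done. Vital signs are scheduled at every visit, so fewer patients should lack them.

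**Step 3: formula.** Let N be the denominator as written, f the share of it with no open-label value, and x the patients with an open-label PCS value.

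- Reported rate = x / N
- Rate among patients tested = x / [N(1 - f)]
- So reported rate = rate among tested × (1 - f)

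**Step 4: numbers.** f is an assumption. For a rate of 5.0% among tested patients:

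- f = 1%: 5.0% × 0.99 = 4.95%
- f = 2%: 5.0% × 0.98 = 4.90%
- f = 5%: 5.0% × 0.95 = 4.75%

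The same in whole patients, taking the planned enrolment of about 760 as an upper bound for N:

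| f | No open-label test | Tested | PCS cases | Cases / tested | Cases / 760 |
|---|---|---|---|---|---|
| 1% | 8 | 752 | 38 | 5.05% | 5.00% |
| 2% | 15 | 745 | 37 | 4.97% | 4.87% |
| 5% | 38 | 722 | 36 | 4.99% | 4.74% |

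The relative understatement is about f whatever the underlying rate. At f = 5% and a rate near 10%, 72/722 = 9.97% becomes 72/760 = 9.47%.

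**Step 5: vital signs.** The same formula applies if the numerator is limited to open-label values, as the introductory sentence of SAP 10.3 and SAP 15.2 require.

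**The case against.** **The effect is small.** Protocol 6.4.1 and 7.9 ask every early discontinuer to attend an ET visit, and protocol 8.4.2.6 includes blood draw, urinalysis and vital signs at that visit. Few patients should have no open-label value. The study is single-arm and descriptive, with no comparator and no hypothesis test on these rates, and SAP 10.2 and 10.3 list each patient with a PCS value. No conclusion is shown to change. All of this stands, and it is why the point is minor.

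**Postbaseline may be meant as open-label.** That may be the intention, but the SAP does not define the word so. SAP 10.2 itself adds the period to the word when it describes the numerator, and SAP section 9 does so for efficacy. The word alone does not carry the limit.

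**Two stronger readings are tempting, and the documents support neither.**

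- *Lead-in abnormalities enter the vital-sign numerator.* A reader might infer this because the numerator sentence names no period. The dilution formula would then fail and the rate could rise: with 36 open-label cases and an assumed 4 lead-in-only cases, (36 + 4)/760 = 5.26%, against 36/722 = 4.99%. But the preceding sentence limits the table to the open-label period, and SAP 15.2 bases PCS determination on open-label assessments. The omission is a matter of drafting.
- *Visit 1 values are charged to open-label treatment.* A reader might infer this from protocol 7.4, which begins: "After a patient signs the ICF at Visit 1 of the Open-label Treatment Period". That sentence describes registration in the response system and does not define an analysis period. Protocol 6.1, 8.2.4, Table 1-1 and the split between 8.4.1 and 8.4.2 all treat Visit 1 as Screening/Baseline. The visit-window tables of SAP 15.1 could not be read in the copy at hand, so nothing is claimed from them.

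**Conclusion.** The point holds for the laboratory rates. Read literally, SAP 10.2 keeps patients with no open-label test in the denominator while allowing only open-label values in the numerator, and so understates the rate by the factor (1 - f). The direction is certain given the numerator as written; the size is not. For an assumed f of 1% to 5%, a 5.0% rate appears as about 4.95% to 4.75%, a loss of about 0.05 to 0.25 percentage points. The documents give no value for f, and the ET visit makes a small one likely.

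SAP 10.3 has the same denominator wording, with a smaller expected effect, and a numerator sentence that should repeat the limit set just before it. The severity is minor: this is an inconsistency with SAP 10.4 and SAP section 9, in primary-objective output, with a modest effect.

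**What to change.** - In SAP 10.2 and 10.3, replace the postbaseline condition in the denominator with the one used for ECGs in SAP 10.4: "and at least 1 assessment during the open-label treatment period".
- In the vital-sign numerator sentence of SAP 10.3, state that the PCS value must fall in the open-label period.

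The cost is a wording change in two SAP sections and the matching change in the table programs. Denominators become slightly smaller. No new data and no protocol amendment are needed.
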